# **Study Description**

Brief Summary:	The study is aim to evaluate the immunogenicity and safety with two groups of participants who will received a seasonal trivalent split, inactivated influenza vaccine (A/H1N1; A/H3N2 and B) or an active comparator (licensed influenza vaccine
Detailed Description:	This is a phase II/III, non-inferiority double-blinded, randomized, controlled trial of immunogenicity and safety with two groups of participants who will received a seasonal trivalent split, inactivated influenza vaccine (A/H1N1; A/H3N2 and B) or an active comparator (licensed influenza vaccine).
	A total of about 945 healthy Thai male and female adult volunteers 18 through 49 years of age; 630 participants will be randomized to receive the GPO Tri Fluvac and 315 will receive an active comparator (a 2:1 ratio) (inclusion of ~7% lost to follow-up).
	Safety will be assessed for all participants through Day 90 after vaccination. Immunogenicity will be assessed in serum samples obtained at baseline and 21 days after vaccination in a subset of at least 586 individuals randomized to study vaccine and 293 active comparator vaccine recipients.

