# **1. PROTOCOL SUMMARY**

Title:	A Phase II/III Double Blinded, Randomized, Controlled, Non-inferiority trial to evaluate the Immunogenicity and Safety of Tri Fluvac, a Seasonal Trivalent Inactivated Split Virion Influenza Vaccine, in Healthy Thai Subjects Aged 18 – 49 Years.						
Protocol #:	GPO Tri Fluvac Vaccine Phase II/III						
Description of Study Design:	This is a phase II/III, non-inferiority double-blinded, randomized, controlled trial of immunogenicity and safety with two groups of participants who will received a seasonal trivalent split, inactivated influenza vaccine (A/H1N1; A/H3N2 and B) or an active comparator (licensed influenza vaccine).						
	A total of about 945 healthy Thai male and female adult volunteers 18 through 49 years of age; 630 participants will be randomized to receive the GPO Tri Fluvac and 315 will receive an active comparator (a 2:1 ratio) (inclusion of ~7% lost to follow-up).						
	Safety will be assessed for all participants through Day 90 after vaccination. Immunogenicity will be assessed in serum samples obtained at baseline and 21 days after vaccination in a subset of at least 586 individuals randomized to study vaccine and 293 active comparator vaccine recipients.						
Study Hypothesis:	Immunogenicity: A single dose of the GPO seasonal trivalent split, inactivated influenza vaccine will induce immune responses measured by HI assay to each of the three vaccine antigens and will be non-inferior to active licensed comparator vaccine.						
	Safety : A single dose of the GPO seasonal trivalent split, inactivated influenza vaccine will be safe and well tolerated in adults 18 to 49 years of age.						
Study	Primary objective						
Objectives.	Immunogenicity:						
	To evaluate the immunological non-inferiority seroconversion rate (using HI assay) and Geometric Mean Titre (GMT) of the GPO seasonal trivalent split, inactivated influenza vaccine compared to active comparator vaccine for each of the three vaccine antigens, three weeks after immunization (Day 21) and at the end of follow-up period (Day 90).						
	Safety:						
	To evaluate the safety profile of a single intramuscular dose of the GPO seasonal trivalent split, inactivated influenza vaccine in adults 18 to 49 years of age.						
	To compare the solicited symptoms, AE and SAE between subjects who will receive GPO trivalent split, inactivated influenza vaccine and those who will receive active comparator vaccine.						

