	Secondary objective APPROVE	E D					
	To evaluate the HI responses at 3 weeks after immunization in participants with OM MIT without pre-existing HI antibody.	TEE					
	MAHIDOL UNIVER	SITY					

Study Endpoints	Primary Immunogenicity Endpoint:
and Statistical Analysis:	Immune responses to the GPO Tri Fluvac and active comparator vaccine at 21 days post-injection will be analyzed by the following:
	- Number and percentage of participants with seroconversion against each of the three vaccine antigens. Seroconversion is defined as a serum HI antibody titer meeting the following four fold rising criteria:
	
 
Pre-vaccination titer <1:10 and a post-vaccination titer measured on Day 21 of ≥1:40; or
 

	
 
Pre-vaccination titer ≥1:10 and at least a four-fold increase in post-vaccination measured on Day 21.
 

	- Geometric mean titers (GMTs) of serum HI antibodies pre- (Day 0) and post-vaccination (Day 21) for each of the three vaccine antigens.
	Note that titers below the lowest limit of quantitation (i.e., below the starting dilution of assay reported as "< 10") will be set to half that limit (i.e., $10/2 = 5$ ). If a titer is reported as greater or equal to the upper limit of the assay, it will be set to that limit.
	The analyses will be performed on the Total Vaccinated cohort (ITT) and According to Protocol (ATP) cohort for immunogenicity. The primary immunogenicity analysis will be based on the ATP cohort.
	- The Total Vaccinated cohort will include all subjects with a documented vaccine administration.
	- The ATP cohort for immunogenicity will include all evaluable subjects (i.e. those meeting all eligibility criteria, complying with the procedures and intervals defined in the protocol, with no elimination criteria during the study) for whom data concerning immunogenicity outcome variables were available for antibodies against at least one study vaccine antigen component after vaccination.
	Primary Safety Endpoints:
	Number and percentage of subjects with solicited local and systemic reactions during the three days post-injection. In addition, all adverse events (AE) and serious adverse events (SAEs), and new onset of chronic diseases (NOCDs) will be collected for the entire study period. Specifically, the following safety parameters will be monitored and analyzed in terms of the number and proportion of participants reporting the following events will be assessed:

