- Day 60 (+14 days): Phone visit for reports of adverse events and ILL if any

ETHICS COMMITTEE FACULTY OF TROPICAL MEDICINE MAHIDOL UNIVERSITY

ตยาลัยม

• Day 90 (+7 days): Blood specimen collection for immune response, follow-up and reports of any AEs/SAEs.

Blood specimens will be collected on Day 0 prior to vaccination, Day 21 and Day 90 following immunization. Serum samples will be separated from whole blood samples for HI assays. Subjects will be asked to report any adverse events and influenza-like illness (ILI) that occur after immunization. Concomitant medication will be collected. At Day 60, there will be a reminder call for reporting any adverse events and ILI. In addition, a throat or nasopharyngeal swab for influenza virus will be performed in those reported ILI. The study schedule and activities are summarized below in Table 2.

Safety will be assessed in all participants through Day 90. The justification for the three month follow-up, rather than six month follow-up is that: 1) in general, the safety of inactivated influenza vaccines is well-established, 2) the phase 1/2 trial showed very limited reactogenicity and no association with unsolicited adverse events.

Immunogenicity will be assessed by HI in a representative subset of at least 586 participants who received vaccine and 293 who receive comparator. In order to select the participants to test in an unbiased way, baseline and post-vaccination blood will be obtained from all the participants. An unblinded statistician will prepare a list of samples to be tested based on a random selection of participants, however neither the laboratory nor the clinical investigators will know the treatment received for each participants.

The study will test a seasonal TIV composed of the following strains:

- A/Michigan/45/2015 (H1N1)pdm-09-like virus
- A/Hong Kong/4801/2014 (H3N2)-like virus
- B/Brisbane/60/2008-like virus

ETHICS COMMITTEE FACULTY OF TROPICAL MEDICINE MAHIDOL UNIVERSITY

APPROVE

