#### **11.2 Sample size calculation**

The sample size calculation was planned for a ratio of 2:1 between GPO Tri fluvac and active comparator vaccine respectively. The SAS 9.4 statistical software, was used to calculate the sample size needed for the study under the assumption of a non-inferiority trial for binary outcome endpoint.

According to the EMA recommendations for the co-primary endpoints, the sample size calculation was basing on the following primary endpoints:

- The difference in seroconversion rate of active comparator vaccine and Seroconversion rate of GPO Tri Fluvac should not exceed 10 percentage points.
- The difference in natural log of mean antibody titer between active comparator vaccine and GPO Tri Fluvac should not exceed 0.405, which is equivalence to the margin for GMT ratio = 1.5.

The sample size calculation was calculated using parameters of the three strains of influenza under the study, including H1, H3, and Flu B. The estimates for seroconversion and standard deviation of natural log of antibody titer were obtained from previous study, phase II study of GPO Tri Fluvac.

Influenza strain	Titer Visit	Treatment Group	Sero- conversion	Mean of ln(titer)	SD of ln(titer)
H1	Day 21	Vaccine	0.88	5.9728	1.08277
Н3	Day 21	Vaccine	0.535	5.36976	1.11926
Flu B	Day 21	Vaccine	0.865	4.75286	1.23306

The sample size calculation for non-inferiority test for proportions was performed with the margin of 0.1, assuming different seroconversion rate of the three influenza strain, and expected difference VED in seroconversion of the two groups is 0.000 with one-sided test alpha level 0.025 and power 0.8. VED Finally the sample size was adjusted for 7% not included in the ATP cohort. The required sample MITTEE size for this co-primary endpoint reached a total of 945 subjects: 630 for study vaccine group and cal MEDICINE 315 for comparator vaccine group.

wo group test of equivalence in proportions (targe unequal n s)				
	H1	H3	Flu B	
Test significance level, α	0.025	0.025	0.025	
(one- sided)				
Standard proportion, $\pi_{S}$	0.880	0.535	0.865	
Equivalence limit difference,	0.100	0.100	0.100	
$\pi_{T}$ - $\pi_{S}$ , $\Delta_{0}$				
Test expected proportion, $\pi_T$	0.880	0.535	0.865	
Expected difference, $\pi_T - \pi_S$ , $\Delta_1$	0.000	0.000	0.000	
Power (%)	80	80	81	
ns	125	293	134	
n T	250	586	276	
Ratio: n T / n S	2.000	2.000	2.000	

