Appendix 06: Listing of Adverse Event	. 78
Appendix 07: Listing of Illness like Influenza (ILI)	. 78
Appendix 08: Listing of Concomitant Medication	. 79
Appendix 09: List of HAI Assay (Flu A H1 Antigen)	. 80
Appendix 10: List of HAI Assay (Flu A H3 Antigen)	. 80

Study Synopsis

Title: A Phase II/III Double Blinded, Randomized, Controlled, Non-inferiority trial to evaluate the Immunogenicity and Safety of Tri Fluvac, a Seasonal Trivalent Inactivated split virion Influenza vaccine, in healthy Thai subjects aged 18 – 49 years.

Protocol #: GPO Tri Fluvac Vaccine Phase II/III

Description of Study Design:

This is a phase II/III, non-inferiority double-blinded, randomized, controlled trial of immunogenicity, safety and preliminary efficacy with two groups of participants who will received a seasonal trivalent split, inactivated influenza vaccine (A/H1N1; A/H3N2 and B) or an active comparator (licensed influenza vaccine).

A total of about 945 healthy Thai male and female adult volunteers 18 through 49 years of age; 630 participants will be randomized to receive vaccine and 315 will receive an active comparator (a 2:1 ratio) (inclusion of \sim 7% lost to follow-up).

Safety will be assessed for all participants through Day 90 after vaccination. Immunogenicity will be assessed in serum samples obtained at baseline and 21 days after vaccination in a subset of at least 630 individuals randomized to study vaccine and 315 active comparator vaccine recipients.

Study Hypothesis:

Immunogenicity: A single dose of the GPO seasonal trivalent split, inactivated influenza vaccine will induce immune responses measured by HI assay to each of the three vaccine antigens and will be non-inferior to active licensed comparator vaccine.

Safety: A single dose of the GPO seasonal trivalent split, inactivated influenza vaccine will be safe and well tolerated in adults 18 to 49 years of age.

Study Objectives:

Primary objective

Immunogenicity:

To evaluate the immunological non-inferiority seroconversion rate (using HI assay) and Geometric Mean Titre (GMT) of the GPO seasonal trivalent split, inactivated influenza vaccine compared to active comparator vaccine for each of the three vaccine antigens, three weeks after immunization (Day 21) and at the end of follow up period (Day 90).

Safety:

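### Protocol 11.2 misstates two safety-precision figures; protocol and SAP also set different numbers for HI testing, with the 7% allowance defined in two ways

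*Protocol*

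**What the plan says.** **Safety precision.** The paragraph before Table 3 in Protocol 11.2 makes two statements about 630 evaluable vaccine recipients. The first is 95% power to see at least one vaccine-associated AE at a true incidence of 1.0%. The second is that, with no related SAE observed, rates of about 0.58% and above can be excluded, which it describes as a one-sided 95% bound. Table 3 shows the same 0.58 for zero events under a two-sided exact 95% heading.

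**Number tested by HI.** Protocol 4.1 states: "Immunogenicity will be assessed by HI in a representative subset of at least 586 participants who received vaccine and 293 who receive comparator". Blood is drawn from everyone, and "An unblinded statistician will prepare a list of samples to be tested based on a random selection of participants". The Protocol Summary and the registry text at the front of both files use the same pair ("subset of at least 586 individuals randomized to study vaccine and 293 active comparator vaccine recipients"). The Study Synopsis in the SAP instead has a "subset of at least 630 individuals randomized to study vaccine and 315 active comparator vaccine recipients".

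**The 7%.** The Protocol Summary describes 945 randomised as "inclusion of ~7% lost to follow-up". Protocol 11.2 says: "Finally the sample size was adjusted for 7% not included in the ATP cohort".

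**Cohorts.** Immunogenicity is analysed on two cohorts, with ATP primary. For the first, "The Total Vaccinated cohort will include all subjects with a documented vaccine administration". The ATP cohort requires, among other things, "complying with the procedures and intervals defined in the protocol, with no elimination criteria during the study". Protocol 11.3.1 defines the ITT population for immunogenicity as all individuals in the trial.

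**The concern.** The safety sentences are the trial's stated ability to detect adverse events. One probability is wrong, and one bound carries a label that its own table contradicts. A reader who relies on the sentence takes away the wrong figure.

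On HI testing, the protocol and the SAP set different minimum numbers. The SAP's minimum is the whole randomised population, so it is not a subset, and a single missing Day 21 sample would make it unattainable. The protocol's minimum equals the evaluable number behind the H3 seroconversion calculation, which sets the sample size.

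The two meanings of the 7% matter because of that equality. A participant without a Day 21 sample cannot be tested at Day 21. A participant who gave a sample but broke an interval or eligibility rule can be tested and then drop out of ATP. If 586/293 is the number left after all such losses, planned power is kept. If it is the number tested before ATP exclusions, there is no reserve. Stopping at the floor while more sera are available would also leave some vaccinated participants without titres for the Total Vaccinated and ITT analyses.

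**Working it through.** **1. Safety probability.** Input from Protocol 11.2: n = 630.

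- P(at least one event) = 1 − (1 − p)^n. At p = 0.01: 1 − 0.99^630 = 0.9982, or 99.8%. The stated 95% does not reproduce.
- Incidence that gives 95% at n = 630: 1 − 0.05^(1/630) = 0.00474, or 0.47%.
- Number needed for 95% at 1.0%: ln 0.05 / ln 0.99 = 298.07, so 299, less than half of 630.

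**2. Zero-event bound, n = 630.**

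- Upper limit of the two-sided exact 95% interval: 1 − 0.025^(1/630) = 0.00584, or 0.58%. This reproduces Table 3.
- One-sided 95% limit: 1 − 0.05^(1/630) = 0.00474, or 0.47%.
- Table 3's other upper limits (0.88, 1.14, 1.84, 2.90) also reproduce as two-sided. The table's heading is right and the sentence's label is wrong.

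**3. Where 586/293 and 630/315 come from.** Inputs from Protocol 11.2: H3 seroconversion 0.535 in both arms, margin 0.10, one-sided alpha 0.025, power 0.80, ratio 2:1.

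- n_S = (1.960 + 0.842)² × 0.535 × 0.465 × 1.5 / 0.10² = 292.9, so 293 comparator and 586 vaccine. This is the plan's figure.
- 586/0.93 = 630.1 and 293/0.93 = 315.05, so 630/315. This is also the plan's figure.

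So 586/293 is the ATP-evaluable requirement and 630/315 the number to randomise. The sample size calculation for H3 is sound.

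**4. H3 power under different testing rules.** Power = Φ(0.10 / √[0.535 × 0.465 × (1/n_T + 1/n_S)] − 1.96).

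| Situation | n_T / n_S in ATP | Power |
|---|---|---|
| All available sera tested, 7% of randomised not in ATP for any reason | 585.9 / 292.95 | 80.0% |
| 586/293 tested, none then leave ATP | 586 / 293 | 80.0% |
| 586/293 tested, 2% then leave ATP | 574.3 / 287.1 | 79.2% |
| 586/293 tested, 5% then leave ATP | 556.7 / 278.4 | 78.0% |
| 586/293 tested, 7% then leave ATP | 545 / 272.5 | 77.1% |

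The share leaving ATP after testing is assumed; the documents do not give it. One intermediate case keeps total loss at the planned 7% of randomised, with 3.5 points from missing Day 21 samples. The share of those tested who then leave ATP is 0.035/0.965 = 3.6%. That gives 564.7/282.4 and power 78.5%.

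**5. Largest number left untested.** 945 − 879 = 66 participants (44 vaccine, 22 comparator), 66/945 = 7.0%. This arises only if nobody lacks a sample and testing stops exactly at the floor.

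**6. Extra assay load.** 66 × 3 time points = 198 sera against 879 × 3 = 2,637 at the floor, or 7.5% more.

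**The case against.** The strongest reply on HI testing is that the protocol's number is a minimum. Testing all 630/315 satisfies it, so a team following the SAP breaches nothing in the protocol. That stands. A reader might infer that the two documents cannot both be obeyed; they can, as long as no sample is missing.

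A reader might also infer that 66 participants are untested by design, so that the Total Vaccinated and ITT analyses cannot be done as defined. The documents do not support this as a general statement. If the planned 7% give no Day 21 sample, about 879 sera remain and the floor is every available serum. The gap opens only if fewer samples are missing and testing still stops at the floor. Nor does the SAP table note about comparing enrolment cases settle whose serum is assayed: it also sits under the demographics table, where it separates enrolled from screen-failed people.

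On the 7%, loss before Day 21 is one route out of ATP, all the sample-size text uses the ATP meaning, and the calculation reproduces. The natural reading of the Protocol Summary is that 586/293 remain after the 7%, which gives 80.0%. That also stands, although the text does not say so.

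The safety slips are conservative: true detection is better than stated, and the one-sided limit is tighter. No sample size or decision rule depends on them. This limits their weight but does not make the sentences correct.

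**Conclusion.** Two statements in Protocol 11.2 are wrong as written. The probability is 99.8%, not 95%, and 0.58% is a two-sided limit, not a one-sided one. Neither signals any shortfall in safety information.

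The HI-testing instruction needs reconciling between protocol and SAP, and the 7% needs one meaning. It would be too strong to say that the trial is underpowered. On the natural reading, H3 seroconversion power is the planned 80.0%. The 77.1% figure needs three things together: no missing samples, testing stopped at the floor, and a full 7% of those tested leaving ATP. No passage describes that combination, and Protocol 5.4.4 expects withdrawal and loss to follow-up to be low. At most 2.9 points are at stake (80.0 − 77.1), and probably less. These figures rest on the plan's own assumptions of 53.5% seroconversion in both arms and a 10-point margin, and on the assumed post-testing exclusion rates shown.

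**What to change.** 1. Restate the safety paragraph in Protocol 11.2. With 630 vaccinees, the probability of at least one event is 99.8% at 1.0% incidence and 95% at 0.47%. With no events, the upper limit is 0.58% (two-sided 95%) or 0.47% (one-sided 95%).
2. Put one HI-testing rule in the Protocol Summary, Protocol 4.1 and the SAP Study Synopsis: test all available Day 0, Day 21 and Day 90 sera from vaccinated participants, with 630/315 planned and about 586/293 expected in ATP. Delete the random selection. This keeps 80.0% at the planned 7% loss however it arises, and leaves no available serum out of the Total Vaccinated and ITT analyses.
3. Define the 7% once, as exclusion from the ATP cohort for any reason, including no Day 21 sample.

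The blood is already drawn from everyone. The cost is at most 198 more sera (7.5% above the floor), and none if the SAP synopsis is already being followed. The rest is text.

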## Table 2: Study Schedule and activities

Procedures	Study Day						
		D0	D7	D21	D60	D90	
			(-3, +7)	(+7)	(+14)	(+7)	
	Screening e	Immunization e					
Informed consent	X						
Assessment of entry criteria	Х	(X) f					
Medical history, AE/SAE, Concomitant medication	Х	(X) f	X	Х	Х	Х	
Vital signs	Х	(X) f	Х	Х		Х	
Urine pregnancy test a	Х	(X) f					
Physical examination a	Х	(X)	(X)	(X)		(X)	
Immunization		X					
Diary card b		X (Day 0-3)	X				
Blood for Immune response (HI Assay) (3ml)		X		Х		Х	
Phone call visit c					Х		
Influenza subtype by RT- PCR d			(X)	(X)	(X)	(X)	

Remark

a. Only at screening, the rest when the history suggested [(x) = Optional as indicated by medical history].

b. Diary card will be provided to the subjects for recording reactogenicity for 3 days after vaccination (Day 0-3) and return to review at Day 7.

c. At Day 60, adverse events and influenza-like illness (ILI) will be followed-up by phone call.

d. Determination of influenza subtype by RT-PCR will be done when the ILI is confirmed [(x) = Optional as indicated].

e. Screening day can be the same day as immunization day (D0)

f. Will be done if immunization is not performed on screening day

(x) Optional

ETHICS COMMITTEE FACULTY OF TROPICAL MEDICINE MAHIDOL UNIVERSITY

APPROVED

## 4.2 Rationale of Study Design

Inactivated influenza vaccine has a well-established safety profile having been prescribed to millions of individuals globally, including children, the elderly, pregnant women, and individuals with chronic disease and immune suppression. Inactivated influenza vaccine also has well established international guidance including quantification of antigen, manufacturing, testing specifications for final bulk and final products, and requirements for national control authorities [30]. Because of predictable immunogenicity, dose finding studies of traditional, non-adjuvanted inactivated influenza are often not required. Furthermore, an immunogenicity study in lieu of an efficacy study as measured by HI (the surrogate endpoint) are common practice for inactivated influenza vaccines.

## 4.3 Study sites

This study will be conducted at Vaccine Trial Centre or its mobile sites, Faculty of Tropical Medicine, Mahidol University.

# 4.4 Study Product Descriptions

## 4.4.1 Acquisition

GPO will provide both the study vaccine and comparator for this trial. The comparator is a licensed inactivated influenza vaccine.

The investigator or qualified designated staff member will be personally responsible for vaccine receipt and management. GPO will determine with the investigator or the designated staff member, the date(s) and time(s) of delivery of vaccine to the study clinic. Study vaccine, manufactured by GPO, and comparator will be supplied to the study clinic by GPO under controlled temperature conditions.

